The proposed study will test the efficacy of the AR app and assess key constructs related to optimizing future implementation. Utilizing a hybrid design in partnership with the Florida Tobacco Quitline, the study will test if the addition of extinction trials via the AR app improves cessation outcomes compared to quitline alone. Quitlines are a low-cost, easily scalable, standard of care treatment option for smoking cessation, employing both behavioral counseling and pharmacotherapy. Nonetheless, smoking abstinence via quitline treatment is modest (~15%) and would likely increase if paired with other theoretically-based treatment components.

Current smokers (N=2072) will be recruited via the quitline and randomized to one of two intervention arms: quitline only (QLO) or quitline plus the AR app (QL+AR). After achieving 48 hours of continuous self-reported abstinence, participants in the QL+AR condition will begin cue-exposure treatment. Although the AR app is designed to be sufficient, participants will have the option of contacting an App coach for app assistance. Abstinence, craving, and nicotine replacement therapy (NRT) will be monitored via daily diary across both conditions. The primary outcome is biochemically-confirmed abstinence at 6 months after baseline survey completion.

Aim 1. Update the existing AR app to be an engaging, user-friendly treatment tool, and verify user satisfaction.
Aim 2. Test efficacy of QL+AR over QLO & explore potential moderators and predictors of treatment effects.

- a. Hypothesis: QL+AR participants will demonstrate higher tobacco abstinence rates six months post-baseline than will QLO participants.
- b. Potential moderators of interest include sex, nicotine dependence, trait cue reactivity, smoking status during treatment, quitline use, and NRT use. Potential predictors within the QL+AR arm include initial cue reactivity, extinction magnitude and latency, indices of treatment engagement, and App coach use.

Aim 3. Evaluate treatment implementation to guide future quitline adoption, including:

- a. Cost-assessment and incremental cost-effectiveness analyses comparing QL+AR with QLO.
- b. Examine treatment engagement and acceptability among those in QL+AR. This will include evaluation of the App coach.
- c. Identify facilitators and barriers to incorporating AR treatment into quitline services via qualitative interviews with quitline supervisors, App coaches, and participants.

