The primary goal of Aim 2 is to test the incremental efficacy of the AR app when added to standard tobacco quitline services. We will recruit and randomize participants to one of two treatment arms: (1) quitline only (QLO) or (2) quitline plus the AR app (QL+AR). In the interest of rapid dissemination and implementation pending positive findings, we have designed procedures with future scalability in mind. Participants will be recruited via the Tobacco Free Florida Quitline and referred to the study team via quitline enrollment agents. Participants who return a baseline questionnaire will be directed to download the app on their personal device and will complete the study. The primary outcome will be biochemically-confirmed tobacco abstinence assessed at around 6 months in a subset of participants.

Participants and Recruitment (see 3.2 above)

Randomization

Block randomization (block sizes=8) will be used to assign 2072 enrolled participants to one of the two conditions. The randomization order will be generated by [name] and implemented within REDCap.

Quitline Services

All study procedures have been developed in close coordination with Tobacco Free Florida, the Florida Department of Health, and RVO Health, the quitline contractor will oversee all aspects of the quitline, including supervising staff to coordinate project activities, modification of quitline software to support the screening and referral of callers, and management of data collection by quitline staff.

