Follow-up questionnaires will be sent to all participants via REDCap around 5 weeks and 6 months after-baseline completion. A subset of participants (40%, approximately 100) who self-report cigarette smoking abstinence at around 6 months will be mailed a saliva collection kit for cotinine-based biochemical confirmation of abstinence. A subset of participants (n=40) from QL+AR will complete a phone interview at the end of treatment, as will a subset of quitline supervisors (n=10) and all App coaches.

Compensation and Retention

For completion of measures at baseline, and around 5 weeks and 6 months after baseline survey completion, participants will receive a \$20 gift card (up to \$60 total). For each week they complete at least 70% of the daily diary questions (5 days), they will receive a \$10 gift card (up to \$50 total). Thus, most participants will be compensated up to \$110. Participants who complete the interview, will be compensated \$20. Participants who return a saliva sample will be compensated \$25.

To aid in retention, the following procedures will take place: collection of full contact information; text reminders and phone calls to follow-up on incomplete surveys; and collection of names and contact information of at least 2 collaterals (i.e., relatives, friends) who can help us reach lost participants.

Treatment Delivery and Fidelity for AR and Quitline Coaching

Although we expect minimal use of App coaches based on the comprehensive app content, we will monitor and assess coaching fidelity. App coaches will be part of the study team. With an eye toward scalability, qualifications will mimic those of quitline coaches (e.g., Bachelor's degree, tobacco abstinent). Training will be manualized and conducted by Drs. [name] and [name], given their experience with exposure-based treatments. Training (8-10 hours) will be a combination of reading, didactics, and role playing. We will develop a measure to assess adherence and competence to be used during the training period. Weekly supervision will occur to ensure App coaching is delivered consistently. Coaches falling below performance

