indicator of treatment engagement. Primary treatment engagement variables of interest that are linked to our theoretical model of extinction and that are related to increased abstinence include: greater completion of the AR sessions (e.g., multiple times per day over several days), conducting the AR sessions in several different locations (to increase generalizability of extinction), and less use of avoidance strategies during the AR sessions (e.g., using distraction or other behaviors to avoid experiencing craving). Avoidance strategies will be assessed at the 5 week survey via a checklist of avoidance strategies and the frequency that they occurred during AR sessions. We will also collect self-reported treatment satisfaction using a modified version of the Client Satisfaction Questionnaire (Attkisson & Greenfield, 1994), the SUS (Brooke et al., 1996; Lewis & Sauro, 2009), and unique items to assess features and functions of the app and the AR experience, including the App coach. Extinction magnitude (degree of craving reduction over time) and latency (time to meeting extinction criteria) will also be derived. For participants who never achieved abstinence during the 5 weeks of app use, thus, never completed AR sessions, versions of the follow-up surveys will omit items specifically related to AR use. For participants who achieved abstinence, but did not complete more than 4 AR sessions, there will be questions at the 5-week survey regarding barriers to completing the AR sessions.

Quitline Usage and App Coaching. Basic information on participant interactions will be provided to the study team from the quitline, including call completion dates, quit status (planned and actual quit dates), and NRT that was shipped. For those in QL+AR, we will track calls completed with an App coach.

Tobacco Abstinence. The primary outcome measure will be 7-day point prevalence abstinence (defined as self-report of no combustible tobacco use in the past 7 days; Piper et al., 2020) around 6 months post-baseline. Reported abstinence will be confirmed in approximately 40% of self-reported abstinent participants using a saliva cotinine level cut-off of <10 ng/ml (Benowitz et al., 2020). Cotinine analysis using ELISA assay will be conducted by Salimetrics (Carlsbad, CA).

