5. STATISTICAL CONSIDERATIONS

Data Management and Statistical Considerations for Aim 1

Compliance will be calculated for the completion of AR urge and daily diary questions. We will also observe the use of various features to determine general use/engagement. The SUS will be scored according to scale instructions, with an expected mean above 68. Interview responses will be reviewed for common themes. Modifications to the app will be made based on these findings. In the unlikely event that major changes need to be made based on participant feedback, we will repeat the procedures for this aim to gather additional feedback on the revised app. Any major changes will be field tested in a similar manner prior to the onset of the RCT in Aim 2.

Data Management and Statistical Considerations for Aims 2 and 3

Overview of Data Management and Statistical Considerations for Aim 2

Based on abstinence rates from quitline/telephone counseling (Fiore et al., 2008; Matkin et al., 2019; Pinerio et al., 2020), the estimated abstinence rate around 6 months for the QLO condition is 10%. With 1036 randomized to each condition, power was calculated for the 725 participants expected to achieve 48-hours of abstinence in each condition (to activate the AR app). Power $\geq .80$ to detect an abstinence rate of at least 15% (OR = 1.59) in the QL+AR condition using alpha = .05, a 2-sided test, and allowing 5% of variance in abstinence rates to be accounted for by other variables. Treatment group differences in baseline measures will be assessed and any variable with a group difference of $p < .10$ will be incorporated into analyses focusing on

intervention effects. To manage missing data, multiple imputation under the Missing at Random assumption will be applied using a Markov Chain Monte Carlo method. The primary statistical analysis for Aim 2 will use logistic regression to compare biochemically-confirmed abstinence rates at the 6-month assessment between conditions. A parallel analysis will be performed to evaluate efficacy for all enrolled (N=2072; i.e., beyond those who exhibit the required 48-hour abstinence to engage the AR intervention). A second test of effectiveness will use generalized estimating equations (GEE) with both the 5-week and 6-month abstinence as the outcomes. Please see the Statistical Design and Power attachment for additional details on our statistical approach.

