Aim 2a. The primary test of the efficacy of QL+AR over QLO will use logistic regression on biochemically-confirmed abstinence around 6 months after baseline survey completion. This will be performed on the 20 imputed data sets using those participants who exhibited 48 hours of abstinence (n=1450). The model will include demographics and smoking-related variables that were found to uniquely predict self-reported abstinence at 6 months based on preliminary analyses. A parallel analysis will be performed to evaluate efficacy for all enrolled (N=2072; i.e., beyond those who exhibit the required 48-hour abstinence to engage the AR intervention). A second test of effectiveness will use generalized estimating equations (GEE) with both the 5-week and 6-month abstinence as the outcomes. This approach permits evaluation of a change in abstinence from around 5 weeks to 6 months and an assessment of the intervention at around 5 weeks in the context of the primary outcome (using a timespecific contrast).

Aim 2b. Prospective moderators of the QL+AR intervention will be explored, separately, by extending the analyses described above through the inclusion of the moderator and the moderator x intervention as predictors of the dependent measure. A significant interaction term supports the variable as a moderator, which will be explored by assessing condition differences for each level of categorical moderators and for levels of continuous moderators created via median splits, tertiles, or quartiles. The following baseline measures will be evaluated: sex, nicotine dependence, trait cue reactivity, smoking status during treatment, quitline use, and NRT use.

Prospective predictors of the AR intervention will be evaluated using only participants from the QL+AR arm. Similar to the analyses described above, AR-related variables will be added to a logistic regression model of abstinence at around 6 months that includes demographics and baseline smoking-related variables found to be predictors of abstinence among QL+AR participants. The following variables will be explored: initial cue reactivity, extinction magnitude and latency, indices of treatment engagement, and App coach use.

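### The primary outcome is biochemically confirmed abstinence in some sections and self-reported abstinence in another; with about 40% of abstainers tested and no coding rule for the rest, it is not uniquely derivable

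*Combined protocol and SAP*

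**What the plan says.** Four places make the confirmed outcome primary:

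- Section 1, Specific Aims: "The primary outcome is biochemically-confirmed abstinence at 6 months after baseline survey completion".
- Section 4.3, Project Overview for Aims 2 and 3: the primary outcome is "biochemically-confirmed tobacco abstinence assessed at around 6 months in a subset of participants".
- Section 5, overview for Aim 2: the primary analysis will "use logistic regression to compare biochemically-confirmed abstinence rates at the 6-month assessment between conditions".
- Section 5, Analytic Plan, Aim 2a: the primary test "will use logistic regression on biochemically-confirmed abstinence around 6 months after baseline survey completion". It is run on 20 imputed data sets for the 1450 participants expected to reach 48 hours of abstinence, with a parallel analysis of all 2072.

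Section 4.4 (Tobacco Abstinence) defines a different variable: "The primary outcome measure will be 7-day point prevalence abstinence (defined as self-report of no combustible tobacco use in the past 7 days". It then adds: "Reported abstinence will be confirmed in approximately 40% of self-reported abstinent participants using a saliva cotinine level cut-off of <10 ng/ml". Section 4.3 (End of Treatment and Follow-up) matches that share: "A subset of participants (40%, approximately 100) who self-report cigarette smoking abstinence at around 6 months will be mailed a saliva collection kit".

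Aim 2a mixes the two variables. It models confirmed abstinence but selects covariates by how well they predict self-reported abstinence.

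The missing-data text in Section 5 refers to missing surveys and to smoking status at 5 weeks and 6 months. It does not mention cotinine or confirmation status. It adds a missing-not-at-random adjustment in the direction of smoking. The supplied documents do not say how the 40% are chosen, or how an untested abstainer, an unreturned kit or a cotinine of 10 ng/ml or more is coded.

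**The concern.** Self-reported and confirmed abstinence are different variables, and the second is measured in fewer than half of those for whom it matters. Two analysts who follow the plan faithfully could fit the primary regression to different outcomes and report different rates and p-values.

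If untested abstainers count as abstinent, the result is mostly self-report under a confirmed label. If their status is imputed, the stated power does not carry over in full. If the adjustment toward smoking were also applied to them, people who reported abstinence and were left untested by design would be shifted toward smoking. The choice should not stay open until outcome data are seen.

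**Working it through.** **Inputs from Section 5 (Sample Size and Study Power Analysis).** 1036 randomized per arm, of whom 725 are expected to reach 48 hours of abstinence. Rates are 10% vs 15% in that set and 7% vs 10.6% in all randomized. The test is two-sided at 0.05, with 5% of variance explained by other variables. From Sections 4.3 and 4.4: about 40% of self-reported abstainers are tested.

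**Step 1: reproduce the stated power.** Two-proportion test with pooled variance, and n reduced by 5% for the covariates:

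- z = [(p2 − p1)√n − 1.96√(2p̄(1 − p̄))] / √(p1(1 − p1) + p2(1 − p2)).
- 48-hour set: n = 725 × 0.95 = 689. z = (1.312 − 0.917)/0.466 = 0.848, so power is 0.802.
- All randomized: n = 1036 × 0.95 = 984. z = (1.129 − 0.785)/0.400 = 0.861, so power is 0.805.

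Both agree with the plan. They assume that every abstainer in the planning rates is an event and is observed.

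**Step 2: count the untested.**

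- 48-hour set: 725 × (0.10 + 0.15) = 181 abstainers. Tested: 0.40 × 181.25 = 72.5. Untested: 0.60 × 181.25 = 108.75, about 109.
- All randomized: 1036 × (0.07 + 0.106) = 182 abstainers, of whom about 73 are tested.

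**Step 3: power under different codings, 48-hour set.** The documents give no confirmation rate, so a share c of 90, 80 or 70% is assumed in both arms, with every kit returned and tests that do not confirm counted as smoking. Suppose first that 10% and 15% are self-report rates:

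| Coding | c = 90% | c = 80% | c = 70% |
|---|---|---|---|
| Untested counted as abstinent: rates × [1 − 0.4(1 − c)] | 9.6 vs 14.4%: 0.78 | 9.2 vs 13.8%: 0.76 | 8.8 vs 13.2%: 0.74 |
| Every abstainer tested: rates × c | 9.0 vs 13.5%: 0.75 | 8.0 vs 12.0%: 0.70 | 7.0 vs 10.5%: 0.63 |
| Untested imputed, confirmation pooled over arms | about 0.74 | about 0.66 | about 0.55 |

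The last row is a simulation: 20,000 runs, 689 per arm, 40% tested, 20 imputations from a beta posterior with a 0.5/0.5 prior, log odds ratio, Rubin's rules. It omits the auxiliary variables that the plan would use.

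At c = 80%, the fall from 0.80 to 0.70 is due to imperfect confirmation and would occur with full testing. Only the further fall from 0.70 to about 0.66 comes from testing 40%.

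If instead 10% and 15% are already confirmed rates, full testing keeps 0.80, and pooled imputation gives about 0.79, 0.77 and 0.75. The sample size text does not say which kind of rate was planned.

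**The case against.** The strongest reply is that the text is ambiguous but usable. Section 5 says that primary-outcome analyses run on complete data after multiple imputation, so untested status might be imputed like any other missing value. Alternatively, confirmed abstinence may mean self-report verified in a sample: Section 4.3 speaks of a subset, and Section 4.4 puts the self-report definition and the 40% check side by side. This stands to the extent that a reader who concludes that the outcome cannot be derived at all goes too far. It can be derived in more than one way. Neither reading is stated, and they give different outcomes.

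Section 5 also says: "Please see the Statistical Design and Power attachment for additional details on our statistical approach". If that attachment is separate from the text supplied, it could hold a coding rule. It would not remove the conflict between Section 4.4 and Sections 1, 4.3 and 5.

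The power loss is also easy to overstate. A reader might infer that only tested and confirmed abstainers count, which gives at best 4% vs 6% and power of 0.40; no section proposes that rule. Imputing within arm gives about 0.68, 0.56 and 0.45 at c = 90, 80 and 70% if the planning rates are self-report. That stacks assumptions about the kind of rate, the confirmation share and the imputation model, so it is not relied on here.

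Two side issues are minor. The sentence on generalized estimating equations (GEE) says only abstinence, and the one kit described is at 6 months, so self-report at both times is its natural reading. The figure of about 100 kits exceeds the 73 implied by the planning rates, but it is offered as an approximation and fits 10% and 15% applied to all randomized (1036 × 0.25 × 0.4 = 104).

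**Conclusion.** The concern holds and should be settled before outcome data are seen. The conflict between sections is explicit, and about 60% of expected abstainers (109 of 181 in the 48-hour set) have no cotinine result by design and no coding rule in the supplied documents. The primary outcome is not uniquely derivable.

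The finding does not depend on any assumed confirmation rate; only its effect on power does. If the planning rates are self-report and 70–90% of tests confirm, power is about 0.74–0.78 with untested abstainers counted as abstinent, and about 0.55–0.74 with their status imputed in the simplified pooled model. Part of the latter fall reflects imperfect confirmation rather than partial testing. If the planning rates are already confirmed rates, the loss is small. The stated power calculation is not itself in error.

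**What to change.** Before outcome data are seen, name one primary outcome and use it in Section 1, Section 4.3 (Project Overview), Section 4.4 and throughout Section 5. State in the sample size text whether 10% and 15% are self-reported or confirmed rates.

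**Cheapest route.** Make self-reported 7-day point-prevalence abstinence primary, as Section 4.4 has it. Draw the 40% saliva subset at random within each arm, and report it by arm as a validation and a pre-specified sensitivity analysis. This costs wording and a random draw, with no more assays. Its downsides are that the headline result is no longer called biochemically confirmed, and that the by-arm comparison of confirmation is imprecise. At 80% confirmation, the 95% half-width is 1.96√(0.16/29 + 0.16/43.5) = 0.19 with 73 tests and 1.96√(0.16/40 + 0.16/60) = 0.16 with 100.

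**If the confirmed outcome is kept.** Pre-specify how untested, unreturned and discordant results are coded or imputed, exempt abstainers untested by design from the adjustment toward smoking, and restate the power.

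**Testing every abstainer** is a further option. It needs about 109 more kits (109 × $25 = $2,725 in compensation at the plan's rate per returned sample). If 100 kits is 40% of abstainers, it needs 100/0.4 − 100 = 150 more ($3,750). Assay cost is extra and is not given.

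Under any option, state that the GEE analysis uses self-report at both times, and say which version of the outcome the cost-effectiveness analysis (Aim 3a) uses.

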Data Management. Baseline, 5-week, and 6-month survey data will be exported from REDCap as .CSV files, which will be read into SAS version 9.4 (SAS Institute, Cary, NC) on a weekly basis during data collection. Data review and primary data analyses will be performed using SAS version 9.4. [name] will oversee the data management, provide the PIs with reports and summaries on a regular basis, and perform the final analyses.

Sample Size and Study Power Analysis. The primary statistical analysis for Aim 2 will use logistic regression to compare abstinence rates at the 6-month assessment between QL+AR and QLO conditions. Preliminary analyses will be used to identify demographics and tobacco history variables that predict either missing surveys or abstinence around 5 weeks and 6 months. These variables will be used in a multiple imputation model to manage missing data. Based on abstinence rates from quitline/telephone counseling (Fiore et al., 2008; Matkin et al., 2019; Pinero et al., 2020), the estimated 7-day point prevalence abstinence rate around 6 months for the QLO condition is 10%. With 1036 randomized to each condition, power was calculated for the 725 participants expected to achieve 48-hours of abstinence in each condition (to activate the AR app). Power $\geq .80$ to detect an abstinence rate of at least 15% (OR = 1.59) in the QL+AR condition using alpha = .05, a 2-sided test, and allowing 5% of variance in abstinence rates to be accounted for by other variables. A comparable analysis using all 2072 randomized participants (the 1450 who do achieve 48-hours of abstinence plus the 622 who do not) will have lower expected abstinence rates. Estimating that 7% of all QLO participants will be abstinent, power $> .80$ to detect an abstinence rate of at least 10.6% for QL+AR (OR = 1.57) using alpha = .05, a 2-sided test, and allowing 5% of variance in abstinence rates to be accounted for by other variables.

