Data Analysis Overview. Descriptive statistics will be used to review all variables in the study prior to hypothesis testing. Data transformations will be made as needed. Treatment group differences in baseline measures will be assessed and any variable with a group difference of $p < .10$ will be incorporated into analyses focusing on intervention effects. All analyses described below will be performed for those who achieved 48 hours of self-reported abstinence (n=1450) as well as the full sample of those enrolled (N=3590). The former is relevant to assessing the efficacy of the app specifically, whereas the latter will reflect the overall incremental effectiveness of the app from the perspective of the quitline. Full-sample versus AR-sample differences in baseline measures will be evaluated.

To manage missing data, multiple imputation under the Missing at Random assumption will be applied using a Markov Chain Monte Carlo method (Schafer, 1997) via PROC MI in SAS, given the expected nonmonotonic missing data patterns and the expected large number of auxiliary variables (e.g., baseline measures that predict smoking status at follow-up) to be determined by preliminary analyses. The imputation model will

include smoking status around 5 weeks, which is expected to be a primary predictor of smoking status around 6 months.

In addition, any other measures acquired around 5 weeks that are unique predictors of missingness or smoking status around 6 months will be included in the imputation model. Finally, a post hoc approach (Rubin, 1987) will address the possible influence of Missing Not at Random. As done in recent studies (e.g., [name] et al., 2016; Martinez et al., in press), the post hoc adjustment will be small-to-medium in size (akin to Cohen's $d=0.35$) in accordance with missing implies smoking. Twenty data sets will be generated. Therefore, all analyses of the primary outcome will be performed on complete data sets (i.e., intent-to-treat) following multiple imputation.

Analytic Plan for Addressing Specific Aims.

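### The primary efficacy test is confined to participants who report 48 hours of abstinence after randomisation, so it is not intent-to-treat as labelled; the full sample is also defined inconsistently

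*Combined protocol and SAP*

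**What the plan says.** **Primary population.** Section 5, Aim 2a, specifies logistic regression on biochemically confirmed abstinence at about 6 months: "This will be performed on the 20 imputed data sets using those participants who exhibited 48 hours of abstinence (n=1450". The sample-size text matches this: "power was calculated for the 725 participants expected to achieve 48-hours of abstinence in each condition (to activate the AR app".

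**Label.** The Data Analysis Overview in Section 5 states that "all analyses of the primary outcome will be performed on complete data sets (i.e., intent-to-treat) following multiple imputation".

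**Full sample.** Aim 2a adds: "A parallel analysis will be performed to evaluate efficacy for all enrolled (N=2072". The overview gives each population a purpose: "The former is relevant to assessing the efficacy of the app specifically, whereas the latter will reflect the overall incremental effectiveness of the app". The full sample is described in three ways:
- Sample Size and Study Power Analysis: "A comparable analysis using all 2072 randomized participants (the 1450 who do achieve 48-hours of abstinence plus the 622 who do not".
- Data Analysis Overview: "as well as the full sample of those enrolled (N=3590".
- Aim 2a: all enrolled, 2072.

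**Order of events.** Section 3.2 places randomisation after consent. The baseline survey follows, then the app link, which is withheld from people reporting more than 7 days of abstinence. Enrolment is counted from app download. Section 4.3 (Randomization) instead assigns participants who are already enrolled. The 48 hours are self-reported in the app (Sections 4.2 and 4.3).

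**Hypothesis.** Aim 2a in Section 1 compares the QL+AR and QLO arms, with no 48-hour condition.

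**The concern.** Randomisation makes the two arms comparable as assigned. A subset formed by something participants do and report afterwards does not inherit that protection. Imputing missing outcomes inside the subset completes its data; it does not bring back the people the subset excludes. The main efficacy claim would therefore rest on a comparison that randomisation does not protect, under a label saying that it does.

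The arms can differ before the 48-hour criterion is met in three ways:
- No blinding to arm is described.
- Reporting 48 hours unlocks the AR features in QL+AR only.
- Section 4.3 describes a progress display in the QLO app, while the QL+AR app at first carries only the diary questions.

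Any of these could change who attains, or who reports attaining, the criterion. The plan also does not say which result governs if the two analyses disagree. The fallback is unclear too: if enrolment means app download, an analysis of everyone enrolled can itself omit randomised people.

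**Working it through.** **Counts.** 1036 × 0.70 = 725.2 per arm; 2 × 725 = 1450; 2072 − 1450 = 622; 622/2072 = 30.0% excluded. For the full sample, 1450/2072 = 70.0%, which matches the attainment expected in Section 4.2. By contrast 1450/3590 = 40.4%, and 0.70 × 3590 = 2513, not 1450. The figure 3590 fits none of the plan's other numbers.

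**Formula.** P(significant for AR) = Φ((d − 1.96·SE0)/SE1), where d is the QL+AR rate minus the QLO rate, SE0 is the pooled and SE1 the unpooled standard error. Each n is multiplied by 0.95 for the plan's 5% variance allowance.

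**The plan's own figure.** With 725 per arm and 10% v 15%: d = 0.05, SE0 = 0.01782, SE1 = 0.01777, so (0.05 − 0.03493)/0.01777 = 0.848 and power is 0.802. The odds ratio is (0.15/0.85)/(0.10/0.90) = 1.588. Both agree with the stated power of at least .80 and OR of 1.59.

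**Illustration: unequal attainment.** The documents give only a common 70%, so every arm difference here is an assumption. QLO attainment is held at 70%, with a 10% abstinence rate in the QLO subset and 1036 randomised per arm. *Marginal reporters* are people whose 48-hour report depends on arm; m is their 6-month abstinence rate.

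QL+AR attainment 75%. The QL+AR subset rate is (0.105 + 0.05m)/0.75 under the planned effect and (0.07 + 0.05m)/0.75 under no effect:

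| m | Rate, planned effect | Power | Rate, no effect | P(significant for AR) |
|---|---|---|---|---|
| 0% | 14.00% | 0.64 | 9.33% | 0.009 |
| 5% | 14.33% | 0.71 | 9.67% | 0.015 |
| 10% | 14.67% | 0.76 | 10.00% | 0.025 |
| 15% | 15.00% | 0.81 | 10.33% | 0.040 |

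QL+AR attainment below 70%, no true effect, 7% abstinent in each arm, all of them attainers:
- 65%: 0.07/0.65 = 10.77% v 10%; P(significant for AR) = 0.067.
- 60%: 0.07/0.60 = 11.67% v 10%; P(significant for AR) = 0.160.

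**All randomised participants, 1036 per arm.**
- The plan's 7% v 10.6%: d = 0.036, SE0 = 0.01277, SE1 = 0.01274; power 0.805, consistent with the stated value above .80.
- 7% v 10.5% (0.70 × 15%): power 0.785.
- The 7% equals 0.70 × 10%, so it assumes no abstinence among non-attainers. If a share q of them is abstinent in both arms (assumption), the rates are 0.07 + 0.3q v 0.105 + 0.3q. For q = 2%: 7.6% v 11.1%, power 0.761. For q = 5%: 8.5% v 12.0%, power 0.726.

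**The case against.** The strongest defence is that nothing is hidden. The subset is pre-specified, powered and given a stated purpose, and the full-sample analysis is planned and powered alongside it. The 48-hour criterion is the same in both arms, and AR content is locked until it is met. The intent-to-treat parenthesis follows a paragraph on imputation and may have been meant only to describe missing-data handling. The figure 3590 is a single outlier against 2072 everywhere else.

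Much of this stands, and it rules out several stronger readings that a reader might infer:
- *That the subset is selected on response to AR.* It is not: first attainment precedes any AR exposure.
- *That no full-sample analysis exists, or that the ranking is unstated.* Aim 2a names the subset primary and the full sample parallel.
- *That bias is demonstrated, or has a known direction.* The unlock could raise reporting in QL+AR and the progress display could raise it in QLO. The illustration moves both ways.
- *That 3590 is a real target.* The recruitment, randomisation and power text all use 2072.

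The defence does not rescue the label, which is applied to every analysis of the primary outcome, including one that excludes 30% of those randomised. Nor does prespecification make a subset defined after randomisation a comparison of the randomised groups.

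A further fair objection is that the all-randomised analysis can fall below 0.80 power on plausible inputs. That is correct, and it belongs in the stated cost of the change.

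**Conclusion.** The plan is wrong as written on two points. First, the primary efficacy test is run in a subset defined by a self-report after randomisation (1450 of 2072 expected), so the intent-to-treat label does not apply to it, and its population is narrower than that of the Aim 2a hypothesis. This follows from the text alone and needs no modelling. Second, the full sample has conflicting counts (2072 and 3590) and conflicting definitions (randomised, or enrolled at app download), and Sections 3.2 and 4.3 disagree on whether enrolment precedes randomisation.

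The size of any bias is unknown. Under the assumed attainment differences, P(significant for AR) with no true effect lies between 0.009 and 0.160 against a nominal 0.025. Subset power with the planned effect lies between 0.64 and 0.81 at 75% attainment. If attainment and reporting do not depend on arm, the subset comparison would not be biased by this route, but the plan cannot assume that in advance. The ranking should be settled before outcomes are analysed, so that the choice cannot look data-driven.

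**What to change.** 1. In Section 5 (Overview for Aim 2, Sample Size and Study Power Analysis, and Aim 2a), make the already planned logistic regression on all randomised participants, analysed as assigned, the primary test. State that it governs the efficacy claim if the two analyses disagree.
2. Keep the 48-hour subset as a secondary app-efficacy analysis without the intent-to-treat label, and report 48-hour attainment by arm.
3. Define the full sample as all randomised participants, whether or not they download the app. Correct 3590, and reconcile the order of randomisation and enrolment in Sections 3.2 and 4.3.
4. Restate power for the new primary test: 0.805 at 7% v 10.6%, 0.785 at 7% v 10.5%, and about 0.76 or 0.73 if 2% or 5% of non-attainers are abstinent in both arms (assumption).

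**Cost.** Re-ranking is a change of wording, since both analyses are already planned. The estimate becomes the diluted programme effect rather than the effect among those able to start AR, and power may sit somewhat below 0.80. Including everyone randomised also adds people who never return the baseline survey. Follow-up is timed from that survey, and the imputation model is to "include smoking status around 5 weeks, which is expected to be a primary predictor of smoking status around 6 months", so the plan needs to say how their missing outcomes are handled. The documents do not give the number of such people, so no figure is attached to this cost.
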